Table 2 shows the actual allocations for the overall sample of participating schools and by TL region. In total, 101 schools were allocated to the control condition. A total of 100 schools were allocated to the intervention group. The numbers of schools in the trial varied by the stratification regions, between nine schools in Devon and 24 in South Yorkshire. The randomisation produced as equal an allocation to the intervention and control group as possible among the overall sample of participating schools and across the TL regions. For instance, in Devon, five of the nine schools in the stratum were allocated to the control group, and four were allocated to the Intervention group. In South Yorkshire, an equal number of schools (12) were allocated to each condition.

Table 2. IWM+A randomisation results

² Table 2 refers to two Merseyside TL regions as there are two TLs delivering the training in this area.

		Control group	Intervention (IWM+A) group	Total schools
1	Cambridgeshire	9	9	18
2	Derbyshire	8	8	16
3	Devon	5	4	9
4	Essex & Suffolk	9	9	18
5	Greater Manchester	11	11	22
6	Merseyside (LB)	9	10	19
7	Merseyside (LLS)	9	9	18
8	Nottinghamshire	10	10	20
9	South Yorkshire	12	12	24
10	Sussex	9	8	17
11	West Yorkshire	10	10	20
	Total	101	100	201

Of the 201 schools that were randomised on 29th September 2021 as above, 195 nominated and provided baseline data for all ten selected pupils. Of the 6 schools not providing full data prior to randomisation, 4 schools had nominated and provided baseline data for nine out of ten pupils, while one school did so for six out of ten pupils and the final remaining school did so for four out of ten pupils. Thus, at baseline, the effective sample size was 1,996 pupils out of a theoretical population of 2,010 (201 schools multiplied by ten nominated pupils).

Outcome measures

Baseline measures

Baseline assessment for trial participating pupils *only* will consist of the following tests:

- 1) **Maths Attainment** based on the Early Years Foundation Stage Profile (EYFSP) Numbers, and Shape, Space and Measures subtests.
- 2) **Attention and Behaviour** based on the adapted 15-item SNAP-IV Teacher Attention Rating Scale (Bussing et al., 2008; Swanson et al., 2001).

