Outcome measures section for more detail on the BAS3 and EYSFP). The pupil level BAS3 scores will be age-standardised with a mean of 100 and standard deviation of 15.

To address the primary research question an intention-to-treat (ITT) analysis will be undertaken using multi-level modelling (MLM) with fixed effects and random intercept. In ITT, data is analysed according to the group randomised, regardless of whether the treatment was actually received as intended, and irrespective of withdrawal from the intervention post-randomisation, or deviations in programme implementation. This principle is key in ensuring an unbiased analysis of intervention effects and is in line with the EEF's guidance (see EEF 2018).

To account for the nested nature of the data, a hierarchical linear model with two levels (school, pupil) will be fitted controlling for pre-intervention scores at the pupil level. Following the stratified randomisation, the model will include a term identifying the regions (strata).

Impact will be estimated by fitting the model in equation (1). Equation (1) is known as a 'random intercepts' model because $\beta_{0j} = \beta_0 + u_j$ is interpreted as the school-specific intercept for school j and $\beta_{0j} \sim i.i.d. N(\beta_0, \sigma_u^2)$ is random (it is a number that can take any value):

$$(1) \quad Y_{ij} = \beta_0 + IWMA_j \tau + Z_j \beta_1 + X_{ij} \beta_2 + u_j + e_{ij}$$

Where:

Y_{ij} = BAS3 scores on the number skills subtest for child i in school j ;

β_0 = the cluster-level coefficient for the slope of a predictor on number skills;

$IWMA_j$ = a binary indicator of the school assignment to intervention [1] or control [0];

Z_j = school-level characteristics i.e. the stratifying variable of geographical location (as used for randomisation);

X_{ij} = pupil level characteristics for pupil i in school j , i.e. the pre-intervention EYFSP score;

u_j = school-level residuals and

e_{ij} = individual-level residuals.

The coefficient τ in Equation 1 above will represent the outcome of the trial, with respect to the primary outcome measure. Equation 1 will also be replicated for each of the three secondary outcome measures (see next section).

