⁵ Due to randomisation, bias will only be introduced in τ if age is correlated with effectiveness of the IWM+A treatment (that is if older pupils improve more rapidly in response to the intervention). Whilst generally any omitted variable would introduce bias in all coefficient estimates, bias will not be introduced if the included variable is both uncorrelated with the omitted variable and all other covariates. By virtue of randomisation, treatment assignment should not be correlated with either school-level characteristics, Z_{ij} , or pupil-level characteristics (including age), X_{ij} . Thus the only reason τ would be biased would be if the treatment effect is correlated with age.

⁶ NPD Alias for this variable is: EVERFSM_6_P_[term][yy]. The variable indicates whether the pupil 'has ever been recorded as eligible for free school meals on Census day in any termly or annual Census (including Alternative Provision Census and PRU Census where available) in the last 6 years up to the pupil's current year (not including nursery)'.

The protocol also outlines an additional compliance analysis. This is outlined below (see [Compliance](#)).

Longitudinal follow-up analyses

Longitudinal analysis will be commissioned separately to this trial.

Balance at baseline

A well-conducted randomisation should create groups that are equivalent at baseline, with any imbalance at baseline occurring by chance (Glennerster & Takavarasha, 2013). However, to check for, and monitor, imbalance at baseline in the realised randomisation, baseline equivalence testing will be conducted at the school and pupil level.

At the school level, we will check the balance in the following variables by means of cross-tabulations and histograms that assess the distribution of each characteristic between the control and intervention groups. We will also report associated effect sizes to quantify the magnitude of any observed imbalance (for continuous measures), but will not undertake statistical testing as the initial randomisation necessarily means that any imbalance we observe is due to chance and therefore statistical tests are not appropriate:

- Ofsted ratings;
- Proportion of children eligible for FSM.⁷

At the pupil level, balance will be assessed as above but for the following characteristics:

- Gender;
- Age (in months);
- Prior attainment using the EYFSP;
- SNAP-IV Teacher Attention Rating Scale;
- FSM status for pupils.

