At the time of drafting this SAP, data on both of the school level characteristics and three of the five pupil level characteristics (gender; age; SNAP-IV Teacher Attention Rating Scale) listed above are available for preliminary analysis of balance at baseline.

⁷ Variable used is PNUMFSMEVER: 'Percentage of pupils eligible for FSM at any time during the past 6 years'.

Table 4 documents the balance between schools and pupils in schools allocated to the control and intervention conditions respectively.

Looking at the two school level characteristics first,

Table 4 presents the balance across the intervention and control group with regards to Ofsted ratings and proportion of pupils eligible for FSM. With regards to Ofsted ratings, the proportion of intervention and control schools rated 'Outstanding' (14.3% and 15.0% respectively), 'Good' (67.3% and 71.0% respectively), 'Requires improvement' (13.3% and 11.0% respectively) and 'Inadequate' (5.1% and 3.0% respectively) were similar. Indeed, the largest percentage point difference was observed among schools rated 'Good', but this difference was still quite small at 3.7 percentage points.

Table 4 shows that the proportion of FSM-eligible children at the school level was similar in the intervention and control school (28.0% and 25.2% respectively) – a 2.8 percentage point difference was observed here. The assessment of these characteristics therefore suggests that, at the school level, a balanced distribution across the intervention and control groups was observed following randomisation.

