The pupil level baseline characteristics also displayed a balanced distribution across the intervention and control groups. Along the lines of gender, the proportion of female and male pupils were similar in the intervention (53.0% and 47.0% respectively) and control groups (53.3% and 46.7% respectively). The distribution of pupil age in months was balanced across the intervention and control groups also; the mean age in months in the intervention group was 90.2 while this was 90.4 in the control group; or roughly 7.5 years in both groups. Finally, attention as measured by the SNAP-IV⁸ was also balanced across the intervention and control groups. The mean on the SNAP-IV was 1.14 in both groups, indicating relatively low levels of attentional difficulty on average in both groups. The absence of any meaningful imbalance at baseline in terms of attention was highlighted by the effect size estimate ($g=0.00$) here, as shown in

⁸ SNAP-IV attention ratings are as follows: 0=Not at all; 1=A little; 2=Mostly; 3=Very much. A higher score denotes greater attentional difficulty. The analysis of baseline equivalence was undertaken on continuous data as overall scores were used, derived by taking the mean across the 15-item attention scale.

Table 4.

We conclude that randomisation has resulted in intervention and control groups that are balanced and comparable based on the school and pupil level baseline characteristics available at the time of SAP drafting.

Table 4. Baseline characteristics of groups as randomised

School-level (categorical)	National-level mean	Control group		Intervention (IWM+A) group		
		n/N (missing)	Count (%)	n/N (missing)	Count (%)	
Ofsted rating						
1. Outstanding	10.5	15/100 (1)	15.0	14/98 (2)	14.3	
2. Good	65.8	71/100 (1)	71.0	66/98 (2)	67.3	
3. Requires improvement	16.4	11/100 (1)	11.0	13/98 (2)	13.3	
4. Inadequate	7.4	3/100 (1)	3.0	5/98 (2)	5.1	
School-level (continuous)		n/N (missing)	Mean (SD)	n/N (missing)	Mean (SD)	
Proportion of FSM-eligible children	25.0	101/101 (0)	25.2% (14.7)	100/100 (0)	28.0% (15.3)	
Pupil-level (categorical)		n/N (missing)	Count (%)	n/N (missing)	Count (%)	
Gender						
1. Female		535/1,004 (0)	53.3	526/992 (0)	53.0	
2. Male		469/1,004 (0)	46.7	466/992 (0)	47.0	
Pupil-level (continuous)		n/N (missing)	Mean (SD)	n/N (missing)	Mean (SD)	Effect size [95% CI]
Age (in months)		1,004/1,004 (0)	90.4 (3.8)	990/992 (2)	90.2 (3.7)	N/A

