SNAP-IV Teacher Attention Rating Scale		1,004/1,004 (0)	1.14 (0.75)	992/992 (0)	1.14 (0.77)	0.00 [-0.09 - 0.08]

As data becomes available⁹ on the other characteristics of interest at baseline (additional to above table), we will assess baseline equivalence at the school level and the pupil characteristics as defined above.

In the final report, as above, we will not carry out statistical significance tests to assess balance at baseline, as the premise of statistical testing at baseline does not hold in randomised controlled trials.¹⁰ Instead, a table of the means along with distributions (for continuous variables) or counts with

⁹ EYFSP rating and FSM status will be obtained from the NPD.

¹⁰ Baseline Data. *Consort (2010)*. Retrieved 26 March (2019): <http://www.consort-statement.org/checklists/view/32-consort/510-baseline-data>

percentages (for categorical variables) will be presented, as above (Senn, 1994).¹¹ While EEF guidance for assessing balance at baseline is such that differences in pupil-level pre-tests should be reported as effect sizes, the pre-test measure in this trial that will be used here (the EYFSP) is categorical, thus Hedge's *g* is not appropriate as it relies on data being normally distributed.

Missing data

Missing data can arise from item non-response to any of the primary or secondary outcome measures, or from attrition of participants at school and pupil levels. Even though it is important to include all data, it can be problematic to apply the ITT principle if we are not able to complete follow-up testing for all randomised schools. To better understand the pattern of missing data and its impact on the analysis, we will explore the extent of missingness, and whether there is a pattern in missingness. We will analyse and report missingness for the primary outcome measure (and associated primary analysis); for the secondary outcome measures and the FSM subgroup we will report the extent of missing data using cross-tabulations but not undertake any additional analyses.

As a basic first step in the missing data analysis we will explore attrition across trial arms to assess bias (Higgins et al., 2011). We will provide cross-tabulations of the proportions of missing values on all baseline characteristics (as detailed in the previous section, at both pupil and school level), as well as on the primary outcome measure and secondary outcome measures.

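### Table 4 omits the promised effect size for school FSM (g = 0.19, compatible with chance) and gives SNAP-IV an apparently unclustered interval, while complete baseline covariates go unused for the primary outcome

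*SAP*

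**What the plan says.** In Balance at baseline, the SAP lists Ofsted rating and proportion of FSM-eligible pupils as the school-level variables and says "We will also report associated effect sizes to quantify the magnitude of any observed imbalance (for continuous measures". School FSM is the only continuous one of the two. The rule then carries over to pupil variables: "At the pupil level, balance will be assessed as above but for the following characteristics".

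Table 4 gives school FSM as mean 25.2% (SD 14.7) in 101 control schools and 28.0% (SD 15.3) in 100 intervention schools, with none missing. No effect size is given for it in the table or the text. The text says "a 2.8 percentage point difference was observed here" and infers that "at the school level, a balanced distribution across the intervention and control groups was observed following randomisation". Age in months has N/A in the effect-size column. Only SNAP-IV has an entry, "0.00 [-0.09 - 0.08" (closing bracket left off here). The section ends: "We conclude that randomisation has resulted in intervention and control groups that are balanced and comparable".

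In Primary outcome analysis, Equation (1) contains treatment, the region strata, and one pupil covariate, "i.e. the pre-intervention EYFSP score". Baseline SNAP-IV is used only for the SNAP-IV outcome. FSM enters only as a pupil-level variable in the subgroup interaction. No sensitivity analysis of the primary outcome adds school FSM or SNAP-IV.

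**The concern.** Three things are at issue, in descending order of certainty.

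- **A promised figure is missing.** The statement that school FSM is balanced rests on raw percentage points. Without the SD a reader cannot tell whether 2.8 points is small, and the standardised figure is what the SAP said it would give.
- **The one interval shown looks too narrow.** Schools were randomised and teachers rate the pupils of their own school, so a SNAP-IV comparison between arms should allow for clustering. The SAP's Effect size calculation section says it will do this for the outcome effect sizes.
- **Precision is left unused.** The SAP says EYFSP dates from Reception, has a restricted range, and probably correlates with BAS3 less than the assumed 0.5. Table 3 credits no school-level correlation at all. School FSM (201 of 201 schools) and baseline SNAP-IV (1,996 of 1,996 pupils) are complete and already held.

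What is at stake is transparent reporting of baseline balance and a modest, nearly free gain in precision. Validity is not at stake.

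**Working it through.** **1. Reproduce the SAP's own figures.**

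The difference in school FSM is 28.0 - 25.2 = 2.8 points, as stated.

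MDES with ICC 0.16, pupil-level R² 0.25, school-level R² 0, 201 schools of 10 pupils, and 199 df (multiplier 2.815):
- school part of the variance: 4 × 0.16/201 = 0.00318
- pupil part: 4 × 0.84 × 0.75/2,010 = 0.00125
- MDES = 2.815 × √0.00444 = 0.188, as stated. With zero pre-post correlation it is 0.196, also as stated.

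The school part is 0.00318/0.00444, about 72% of the variance of the treatment estimate. With EYFSP uncorrelated, the pupil part is 4 × 0.84/2,010 = 0.00167 and the share is about 65-66%.

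**2. School FSM effect size** (Table 4; for the school numbers, Randomisation: "In total, 101 schools were allocated to the control condition. A total of 100 schools were allocated to the intervention group").
- Pooled SD = 15.0; d = 2.8/15.0 = 0.187; after the small-sample correction g = 0.186.
- SE = √(201/(100 × 101) + 0.186²/(2 × 201)) = 0.141; 95% CI -0.09 to 0.46.
- Rounding of the printed means allows g from 0.18 to 0.19.
- t = 2.8/(15.0 × √(1/100 + 1/101)) = 1.32 on 199 df. Ignoring stratification, a difference at least this large arises in about 19% of sound randomisations.

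**3. FSM among trial pupils** (Table 3). 403/992 = 40.6% vs 401/1,004 = 39.9%, a standardised difference of about 0.01. The SAP also says pupil FSM status is still to come from the NPD, so these counts may change slightly.

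**4. Age** (Table 4). (90.2 - 90.4)/3.75 = -0.05, with a pupil-level interval of -0.14 to 0.03.

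**5. SNAP-IV interval.**
- Unclustered half-width: 1.96 × √(1/1,004 + 1/992) = 0.088. An unrounded g between about -0.003 and -0.005 then prints as 0.00 with limits -0.09 and 0.08, which is what Table 4 shows.
- The rounded limits allow a half-width of at most (0.095 + 0.085)/2 = 0.090. A clustered interval that narrow needs a design effect below (0.090/0.0877)² = 1.053, so an ICC below 0.053/8.93 = 0.006.
- With mean cluster size 1,996/201 = 9.93, half-width = 0.0877 × √(1 + 8.93 × ICC). This gives 0.121 at ICC 0.10, 0.137 at 0.16 and 0.146 at 0.20. The SAP gives no ICC for SNAP-IV, so the range is assumed.

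**6. What school FSM could do in the primary model.** The SAP gives no correlation r between school FSM and school-mean BAS3. Take its size as 0.2 to 0.5, net of region and EYFSP. The school SD is √0.16 = 0.40.
- Shift from the chance imbalance: 0.186 × 0.40 × r = 0.015 to 0.037 SD, or 8% to 20% of the MDES. If poorer schools score lower, the shift is against the intervention.
- MDES with school-level R² = r² (0.04 to 0.25): 0.185 to 0.170.

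**7. What SNAP-IV could do.** Assume it explains 4% to 9% of the remaining pupil-level variance. With EYFSP at r = 0.5, the MDES goes from 0.1876 to 0.1865-0.1852. With EYFSP uncorrelated, it goes from 0.1962 to 0.1948-0.1931. The gain is 0.001 to 0.003.

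**The case against.** Much can be said for the plan. Strata plus prior attainment is a legitimate prespecified model and contradicts nothing in the SAP. Leaving out a prognostic covariate does not bias a randomised ITT estimate in expectation; footnote 5 argues on similar lines for age. PNUMFSMEVER describes the whole school, whereas the trial analyses about ten low-attaining nominees per school. The SAP reports the MDES under zero EYFSP correlation, calls Table 4 preliminary, and promises a fuller table. No threshold for standardised differences is set that 0.19 would breach, and no decision hangs on the SNAP-IV interval. All of this stands.

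It also rules out several stronger readings:
- A reader might infer that randomisation went wrong or that the treatment estimate is biased. The interval for g includes zero and pupil-level FSM is nearly equal.
- A reader might put SNAP-IV in the same category. It is balanced (g = 0.00), so its omission costs a little precision only. The SAP's description of attention as proximal concerns a mediator and is not evidence that baseline SNAP-IV predicts BAS3.
- A reader might assume that FSM explains up to 30% of school variance. Correlations of 0.2-0.5 imply 4-25%.
- Adding a covariate because it looks imbalanced is the practice that footnote 11 notes is disputed. The case for school FSM must rest on prognosis and completeness.

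What the objection does not remove is the missing effect size, which the SAP promised and had complete data to compute, or the interval that does not match the unit of randomisation.

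**Conclusion.** The point holds as a reporting fault with a modest analysis improvement attached. School FSM differs by g = 0.19 (95% CI -0.09 to 0.46). The SAP's own rule required this to be shown, and it is compatible with chance. The SNAP-IV interval is consistent with ignoring clustering and would be roughly 1.4 to 1.7 times as wide at an assumed ICC of 0.10-0.20. Adding school FSM to the primary model would lower the MDES from 0.188 to about 0.185-0.170 and remove a possible chance shift of about 0.015-0.037 SD. Both ranges rest on an assumed correlation of 0.2-0.5 with school-mean BAS3. SNAP-IV would add only 0.001-0.003. The documents do not support calling the headline model invalid; they support saying that it could be more precise at almost no cost.

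**What to change.** **Reporting.** In Table 4, print g with its 95% CI for school FSM and for age. Replace the word balanced for school FSM with the figure. Recompute the SNAP-IV interval allowing for schools, and state the method and ICC.

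**Analysis.** Before outcomes are seen, prespecify a primary-outcome model that adds school percentage FSM (PNUMFSMEVER) to Z_j and, optionally, baseline SNAP-IV to X_ij. Give prognosis and completeness as the grounds, not the observed difference. Either make this the primary model and keep the strata-plus-EYFSP model as a sensitivity analysis, or, at minimum, do the reverse. The SAP describes the May 2022 testing as still to come, so the choice can be fixed without knowledge of results.

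**Cost.** A few lines of SAP text and data already held. The downside is a small departure from the minimal model, which is retained for comparison with the efficacy trial.

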Baseline assessment was completed prior to randomisation: the Maths Attainment baseline – the EYFSP – was completed when children were in Reception as part of national testing requirements, whereas data on attention and behaviour was collected as part of this trial. The baseline measures are discussed in more detail below.

1) Maths Attainment

To reduce burden on schools it was decided to use existing Maths Attainment data available in the National Pupil Database (NPD). KS1 results would have been preferable given this would parallel the approach in the efficacy trial and the fact that they would be collected in the summer before implementation. However, in light of constraints resulting from the COVID-19 pandemic the 2021 KS1 SATs were cancelled by the Department for Education. Therefore, for this trial the Maths Attainment baseline data is sourced from the EYFSP completed in the 2018/2019 academic year, when the Year 3 children were in Reception. The EYFSP is a nationally administered measure of ability completed by practitioners (i.e. teachers or other qualified school staff) at the end of Reception when children are between the ages of four and five. The EYFSP is divided across the 17 early learning goals (ELGs) of the Early Years Foundation Stage (EYFS). For the purposes of this trial, we use two ELGs related to

Mathematics, namely: Numbers (MAT_G11), and Shape, Space, and Measures (MAT_G12). These scores are assigned by practitioners who are asked to decide whether children are meeting the expected learning levels. The NPD record for the Numbers and Shape, space and measures ELGs contain 1-3 assessment rating, where:

1. Indicates a child who is at the emerging level.
2. Indicates a child who is at the expected level.
3. Indicates a child who is at the exceeding level.

Children who have not been assessed due to long periods of absence or have been exempted are recorded as 'A' in the NPD. In this trial we will combine the score on both ELGs related to math to gain insight in the wider mathematical attainment. The total combined EYFSP score can therefore range from two to six.

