To assess whether there are systematic differences between those who drop out and those who do not – and thus whether these factors should be included in analysis – we will model missingness at follow-up (defined as pupils with missing primary outcome data at endline) as a function of baseline covariates, including treatment. The analysis model for this approach will mirror the multilevel level model specified in Equation (1), with pupils clustered in classes, but the outcome will be a binary variable identifying missingness (where 1=missing; 0=complete) in a multilevel mixed-effects logistic regression model (using Stata's `meLogit` command). We can similarly model missingness at baseline (defined as pupils with missing baseline data, namely missing EYFSP) as a function of endline covariates, including treatment.

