We will follow the protocol for missing data suggested by the EEF (see EEF, 2018). For less than 5% missingness overall from randomisation to final analysis, a complete-case analysis will be employed. This assumes that data are missing completely at random (MCAR), which we will be able to test partially with the model outlined above. For more than 5% missing data overall from randomisation to final analysis, our approach will depend on pattern of missingness. If the pattern of missingness may be unrelated to the treatment effect (e.g., pupil illness, staff changes or COVID-related impacts on testing but not on intervention), then missing data will be assumed MCAR and we will continue with a complete-case analysis. Otherwise, we will adopt a full-information maximum likelihood (FIML) approach. FIML estimates the value of the trial parameter of interest (τ in Equation 1) by maximising the likelihood function in the presence of missing data. We will not supplement this analysis with a separate approach, usually multiple imputation, MI, analysis, as the results of the two have been shown recently to be broadly equivalent (Lee & Shi, 2021). Additionally, in comparison to MI, FIML produces the same results every time, can be estimated in a single model and simulation studies show that it can reduce bias as well as MI (for a detailed discussion of FIML vs MI see Allison, 2012 or Jakobsen et al, 2017). The FIML approach only alleviates bias if pattern of missingness is dependent only on observed variables, namely missing at random (MAR); if the reason for missingness is due to unobserved variables, namely missing not at random (MNAR), then FIML or MI will not improve estimates. Note, however, that MAR and MNAR are not distinguishable based on observed data. If it seems likely data could be MNAR, sensitivity analysis will be conducted and reported alongside headline estimates.

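### Above 5% missing data, complete-case analysis is kept on a test that is not MCAR and has no objective criterion; it also drops pupils who have BAS3 but no EYFSP

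*SAP*

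**What the plan says.** The Missing data section of the SAP sets three branches.

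- Below the threshold: "For less than 5% missingness overall from randomisation to final analysis, a complete-case analysis will be employed".
- Above it, the first question is about cause: "If the pattern of missingness may be unrelated to the treatment effect (e.g., pupil illness, staff changes or COVID-related impacts on testing". The bracket goes on to limit the COVID example to effects on testing and not on the intervention. If the condition is met, "then missing data will be assumed MCAR and we will continue with a complete-case analysis".
- Failing that: "Otherwise, we will adopt a full-information maximum likelihood (FIML) approach".

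The same section plans a model of drop-out: "we will model missingness at follow-up (defined as pupils with missing primary outcome data at endline) as a function of baseline covariates", with treatment among the predictors. Its stated uses are to judge whether such factors belong in the analysis and to test MCAR in part. There is also a conditional safeguard: "If it seems likely data could be MNAR, sensitivity analysis will be conducted and reported alongside headline estimates". No method is given for it.

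On the covariate, the Primary outcome analysis section puts EYFSP into Equation (1). The Baseline measures section notes that some children have no rating: "Children who have not been assessed due to long periods of absence or have been exempted are recorded as 'A' in the NPD". The Missing data section recognises this: "We can similarly model missingness at baseline (defined as pupils with missing baseline data, namely missing EYFSP". It offers to model that missingness but says nothing on how such pupils enter the primary analysis. The sensitivity analysis on including EYFSP is described under Secondary outcome analysis.

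**The concern.** MCAR requires that missingness be independent of both observed and unobserved data. Being unrelated to the treatment effect is a different condition. Pupil illness and staff changes, two of the plan's own examples, can go with lower attainment or with particular schools without any link to how well the intervention works.

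The condition is also only that the pattern may be unrelated, which can be argued for most patterns of loss. The missingness model is planned, but no finding from it is tied to the choice between complete-case and FIML. The analysts would make that choice for the primary outcome after seeing how much was lost and where.

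The missing-EYFSP problem runs through the same rule. Below 5%, complete-case analysis removes a pupil with a measured BAS3 and no EYFSP. Above 5%, a gap that arose in 2018/19 easily counts as unrelated to the treatment effect, so the pupil is removed again. The FIML branch could keep these pupils but is reached only when the trigger fails. The plan itself describes EYFSP as not sensitive and runs its power at zero correlation.

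**Working it through.** **Inputs from the SAP** (Sample size section and Table 3): 201 schools, 1,996 pupils (1,996/201 = 9.93 per school), ICC ρ = 0.16, pupil-level R² = 0.25 (r = 0.5), school-level R² = 0, two-sided alpha 0.05, power 0.80, equal allocation. The SAP gives no missing rate for EYFSP or BAS3, so every rate below is an assumption.

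**Threshold.** 5% of 1,996 = 99.8, about 100 pupils.

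**Reproducing the plan's figures.** MDES = M × √[ρ/(0.25J) + (1 − ρ)(1 − R²)/(0.25Jn)], where M is the sum of the 0.975 and 0.80 quantiles of t on J − 2 degrees of freedom (about 2.815 for J = 201).

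- J = 201, n = 9.93, R² = 0.25: 0.16/50.25 = 0.003184 and 0.63/499 = 0.001263. The root of the sum is 0.06668, giving 0.1877 (SAP: 0.188).
- R² = 0: 0.1964, or 0.1962 with n = 10 (SAP: 0.196).

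**Cost of dropping pupils without EYFSP.** For complete-case, n becomes 9.93(1 − d), where d is the missing fraction. For all pupils kept, n stays at 9.93 and R² becomes R²(1 − d), an approximation.

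| Missing EYFSP (assumed) | Pupils dropped | r = 0.5: complete-case / all kept | r = 0.3: complete-case / all kept | r = 0: complete-case / all kept |
|---|---|---|---|---|
| 5% | 100 | 0.1891 / 0.1882 | 0.1950 / 0.1935 | 0.1982 / 0.1964 |
| 10% | 200 | 0.1907 / 0.1886 | 0.1968 / 0.1937 | 0.2002 / 0.1964 |
| 20% | 399 | 0.1943 / 0.1895 | 0.2010 / 0.1940 | 0.2047 / 0.1964 |
| 30% | 599 | 0.1988 / 0.1904 | 0.2064 / 0.1943 | 0.2105 / 0.1964 |

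**When complete-case analysis misleads.** Simulation of 2,000 trials per case: 201 schools of 10 pupils, ICC 0.16, a continuous baseline with r = 0.5, true effect 0.19. Complete cases were regressed on arm and baseline (Monte Carlo error about 0.0015). The missingness mechanisms are assumed.

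- About 10% of pupils dropped, depending on the pre-randomisation baseline: mean estimate 0.189.
- About 14% of outcomes lost, depending on attainment alike in both arms: 0.190.
- About 12% lost, depending on the baseline in the control arm only: 0.189.
- About 12% lost, depending in the control arm only on a part of the outcome that the baseline does not explain: 0.094.

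Only the last case biases the comparison. It is MNAR given the variables in Equation (1). FIML with those same variables would not repair it; FIML with further baseline variables helps only as far as they carry the missing information.

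**The case against.** The strongest reply is that the MCAR label is wrong but does little harm. Complete-case fitting of Equation (1) conditions on arm, region and EYFSP. If outcome missingness depends only on those, and the model is right, the estimate is valid without MCAR, and FIML with the same variables would give essentially the same answer. The plan also has safeguards: attrition compared across arms, a missingness model that includes treatment and may bring predictors into the analysis, and a conditional MNAR sensitivity analysis. All of this stands. What it leaves open is who decides between complete-case and FIML, and on what result.

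A reader might infer that the primary analysis will rest on a biased subset. Suppose 10% missing in one arm, 20% in the other, and absent pupils 0.3 SD lower: the shift is 0.3 × (0.20 − 0.10) = 0.03 SD, and 0.03/0.188 = 16% of the MDES. The documents do not support this as a consequence of the rule. The inputs are invented, and so large a gap between arms would show in the planned checks and could hardly be called unrelated to treatment. A MAR model without the relevant predictors would leave the bias in place.

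A reader might also infer that dropping pupils without EYFSP breaks intention to treat. The SAP defines that principle as analysis by group randomised, and the exclusion moves nobody between arms. Because EYFSP predates allocation, the comparison among those who remain is unbiased.

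Nor does adjusting for EYFSP gain nothing over leaving it out. With 10% missing, that is so at r = 0 (0.200 against 0.196) and r = 0.3 (0.197 against 0.196). At the planning value of r = 0.5, complete-case with EYFSP is better (0.191 against 0.196).

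**Conclusion.** The point holds in limited form. The trigger above 5% is not MCAR, is worded so that it can usually be met, and is not tied to any result of the missingness model. The choice of primary analysis is therefore left to judgement after attrition is known. The exposure is to predictors of missingness outside Equation (1), and to MNAR. Its size cannot be derived from the SAP, and FIML answers only the first of these, and only if the predictors are included.

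The loss of pupils with BAS3 but no EYFSP is a separate and small matter of precision and representativeness. At an assumed 10% missing, the MDES rises from about 0.189 to 0.191 at r = 0.5, and from 0.196 to 0.200 at r = 0. At 20% the pairs are 0.190 to 0.194 and 0.196 to 0.205. These figures rest on the plan's ICC of 0.16 and on missing rates that the SAP does not give. The change is worth making because it is cheap and closes a discretionary choice in the primary analysis.

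**What to change.** 1. Delete the trigger based on missingness that may be unrelated to the treatment effect.
2. Above 5% missing, always report the FIML (MAR) analysis beside complete-case, and name in advance which is the headline. Include as predictors of missingness SNAP-IV, which Table 4 shows complete for all 1,996 pupils, and the other collected baseline variables. Reporting both avoids a new significance trigger: with the seven baseline characteristics listed under Balance at baseline, treated as independent and each tested at 5%, such a trigger would fire by chance about 30% of the time (1 − 0.95⁷ = 0.30).
3. Keep every pupil with BAS3 in the primary model through a pre-specified handling of missing EYFSP, such as a missing indicator. Randomisation protects this because EYFSP precedes allocation. It does nothing for missing BAS3, which item 2 covers.

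Cost: a few sentences of SAP wording, one extra model run, and one or a few degrees of freedom. The MNAR risk remains and should be acknowledged in the report.
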